#### 14.0 INVESTIGATOR MAINTENANCE OF STUDY RECORDS

The Site PI will be responsible for **maintaining study records** per 21 CFR 812.140(a) and Good Clinical Practice: Consolidated Guidance (ICH, April 1996), Section 4.9.

The Site PI will allow auditing of their clinical investigation procedure(s).

Each investigator will provide a completed Financial Disclosure prior to study initiation and upon request at later time points in the study.

The Investigator is responsible for maintaining medical and study records for every patient participating in the clinical study (including information maintained electronically such as digital imaging). The study center will also maintain **original** source documents from which study-related data are derived, which may include, but are not limited to:

- Clinic progress notes recording patient's medical history and medications
- Medical records regarding AEs, including treatment and clinical outcome
- Results of diagnostic examinations
- Notes of phone calls and/or correspondence indicating investigational site's attempts to contact and follow a study patient at the required follow-up time points until such time a subject is determined to be lost-to-follow-up.

The Investigator must ensure that all study patient records are stored for at least 2 years after the latter of the following two dates: The date on which the investigation is terminated or completed, or the date that the records are no longer required for purposes of supporting a premarket approval application or a notice of completion of a product development protocol. To avoid error, the study site should contact the study sponsor prior to the destruction of study records to ensure that they no longer need to be retained. In addition, the study sponsor should be contacted if the Investigator plans to leave the investigational site so that arrangements can be made for the handling or transfer of study records.

#### 15.0 INVESTIGATOR REPORTS

The Site PI will be responsible for reporting per 21 CFR 812.150(a) and according to applicable IRB/EC requirements and Good Clinical Practice: Consolidated Guidance (ICH, April 1996), Section 4.11.

*NOTE: Reports must identify patients using the study's unique identifier to protect patient's confidentiality.*

The primary responsibility of the investigator is to protect the welfare of the study subjects. Other responsibilities, including adherence to the protocol, are defined in the Investigator Agreement.

#### 16.0 DATA MANAGEMENT

Data will be handled as applicable, per Good Clinical Practice: Consolidated Guidance (ICH, April 1996), Section 5.5. To ensure proper tracking of Case Report Forms, a tracking system will be utilized.

**16.1 Data Entry**

Qualified personnel assigned by the principal investigator and/or the sponsor will perform data entry.

**16.2 Data Back-up**

Incremental computer data backup will be performed on a regular basis. All hard copies of Case Report Forms and media will be stored in a secure location.

**16.3 Confidentiality and Security**

Passwords will be issued to appropriate personnel to insure confidentiality and protection of data.

**16.4 Final Report**

A final report will be completed, even if the study is prematurely terminated.

**16.5 Publication Policy**

After the conclusion of the trial, the results may be prepared and presented at a major meeting(s). The publication of results from any center experience within the trial is not allowed, unless there is written consent from the study sponsor.

**17.0 DEFINITIONS AND ACRONYMS****Case Report Form (CRF)**

Printed, optical or electronic document designed to record all the protocol required information to be reported to the sponsor on each trial subject

**Confidentiality**

Prevention of disclosure, to other than authorized individuals, of a sponsor's proprietary information or a subject's identity (GCP Consolidated Guidance).

**Ethics Committee (EC) / Institutional Review Board (IRB)**

Synonyms. An independent body constituted of medical, scientific and nonscientific members, whose responsibility is to ensure the protection of the rights, safety and well-being of human subjects involved in a trial by, among other things, reviewing, approving, and providing continuing review of trials, of protocols and amendments, and of the methods and material to be used in obtaining and documenting informed consent of the trial subjects (GCP Consolidated Guidance).

**Good Clinical Practice (GCP)**

An international quality standard for conducting clinical trials that is provided by International Conference on Harmonisation (ICH) to protect trial subjects' rights, safety, and welfare, as well as provide integrity to the overall study data.

**Informed Consent**

The process by which a subject voluntarily confirms his or her willingness to participate in a trial, after having been informed of all aspects of the trial that are relevant to the subject's decision to

participate. Informed consent is documented by means of a written, signed and dated consent form (GCP Consolidated Guidance).

**Informed Consent Form (ICF)**

A document disclosing the risks, benefits, and alternatives of a clinical trial and documents the subject's voluntary willingness to participate in a clinical trial.

**Source Data**

All information in original and identified records and certified copies of original records of clinical findings, observations, or other activities in a clinical investigation, necessary for the reconstruction and evaluation of the clinical investigation. Source data are contained in source documents (ISO 14155 and GCP Consolidated Guidance).

**Source Documents**

Original documents, data and records (ISO 14155).

*NOTE: This may be, for example, hospital records, laboratory notes, pharmacy dispensing records, copies or transcriptions certified after verification as being accurate copies, photographic negatives, radiographs, and records kept at the pharmacy, at the laboratories, and at medico-technical departments involved in the clinical investigation.*

## 1 INTRODUCTION

Aerin Medical believes that the benefits demonstrated with the Vivaer Stylus procedure in the Aerin Medical TP258 study, “A Prospective, Multi-Center, Non-Randomized Study to Evaluate Treatment of Nasal Airway Obstruction Using the Aerin Medical Device” may be durable beyond the initial six months of the study in terms of sustained quality of life impact. The TP258 study demonstrated the safety and effectiveness of the treatment procedure to the 26-week endpoint and was the clinical basis for 510(k) clearance of the device by the FDA (K172529 5 December 2017). This prospective follow-up study on a cohort of subjects from the TP258 study collected nasal obstruction symptom evaluations (NOSE) and responses to an Aerin Medical Quality of Life survey at 12, 18 and 24 months after the procedure.

The purpose of this statistical analysis plan is to outline the necessary statistical techniques required to evaluate the efficacy outcome parameters in the Final Report for Clinical Protocol (TP465).

## 2 OBJECTIVE

The objective of the study was to evaluate the long-term durability of benefits associated with the treatment procedure using the Vivaer Stylus for relief from nasal airway obstruction.

## 3 STUDY DESIGN

### 3.1 Overview

This investigation was a prospective extended follow-up study of subjects who had participated in the TP258 multicenter trial to evaluate the safety and efficacy of the Vivaer Stylus. Subjects were followed to the 26-week endpoint in that study. Subjects agreeing to participate in this follow-up study were to provide self-evaluation NOSE and quality of life measures at 12, 18, and 24 months after the treatment procedure. There was no concurrent control population or blinding in either the original TP258 study or in this extended follow-up study.

Self-administered evaluations were scheduled for 12, 18, and 24 months after the treatment procedure. Evaluations could occur in person with study personnel, by phone, or by mail.

### 3.2 Test Device

The Aerin Medical Vivaer® Stylus is a disposable handheld device capable of delivering bipolar radiofrequency energy to tissue and has been used to treat nasal airway obstruction. The device was cleared by the FDA (K172529 5 December 2017) with indication for use in otorhinolaryngology (ENT) surgery for the coagulation of soft tissue in the nasal airway, to treat nasal airway obstruction by shrinking submucosal tissue, including cartilage in the internal nasal valve area.

### 3.2 Population and Sample Size

Subjects who completed participation in the Aerin Medical TP258 study, “A Prospective, Multi-Center, Non-Randomized Study to Evaluate Treatment of Nasal Airway Obstruction Using the Aerin Medical Device” were eligible for inclusion and participation in this study. These subjects had exhibited significant symptoms of nasal obstruction attributed to internal nasal valve dysfunction prior to undergoing treatment with the Aerin Medical Vivaer Stylus and completing 26 weeks of follow-up in the Aerin Medical TP258 study.

The maximum sample size for this extended follow-up of the TP258 study was 49 subjects, the number that completed the TP258 study.

All eligible subjects who provided informed consent and completed at least 1 survey were included in the analysis population. A second nonenrolled population was defined as those subjects enrolled in the TP258 study that chose not to enroll in this extended follow-up study. The purpose of the nonenrolled population was to allow comparison of characteristics of subjects who self-selected to enroll in the follow-up study with those who chose not to enroll in the follow-up study.

## 4 OUTCOME MEASURES

### 4.1 Nasal Obstruction Symptom Evaluation (NOSE)

Nasal valve evaluation is based on clinical observations of signs and symptoms with no easily obtained, reproducible objective measurement techniques of the valve; therefore, the Nasal Obstruction Symptom Evaluation (NOSE) questionnaire was used in the TP258 study as the primary outcome measure and was continued in this follow-up study. The NOSE questionnaire is a validated disease-specific health status instrument used by clinicians to measure the outcome of subjects treated for nasal obstruction. The NOSE survey consists of 5 items, each scored using a 5-point (0 - 4) Likert scale. The 5 item scores are summed and then multiplied by 5 to make a total score range of 0 through 100, where higher scores indicate worse obstruction. Severity of symptoms can be classified as mild (range, 5-25), moderate (range, 30-50), severe (range, 55-75), or extreme (range, 80-100) nasal obstruction, based on responses to the NOSE survey.

Treatment responders were defined in the TP258 study as subjects achieving a 15 point or greater improvement in the NOSE score compared to baseline.

### 4.2 Aerin Medical Quality of Life survey

A 21-item quality of life survey was developed to assess aspects of subjects' current quality of life compared to before the procedure that are typically associated with nasal obstruction and trouble breathing (Figure 1). The first 14 items addressed agreement or disagreement with statements concerning sleep, energy, productivity, emotions, activities, and work. Answers were provided on a 5-point Likert-type scale, Agree Strongly, Agree, Neither agree or disagree, Disagree, Disagree Strongly. The next 4 items addressed the occurrence of health-related symptoms

associated with nasal obstruction. The frequency of occurrence of headaches, sinus infections, sore throat, and post nasal drip were each assessed on a 5-point scale of Very Rarely/Never, Rarely, Occasionally, Frequently, Very Frequently. The last 3 items assess the frequency of use of medications and devices for nasal congestion. The 5-point response scale is Much less frequently, Less Frequently, About the Same, More Frequently, Much More Frequently.

**Please indicate your level of agreement with the following statements:**

*Compared to before I had the Aerin Medical Nasal procedure, I have experienced*

		Agree Strongly	Agree	Neither agree or disagree	Disagree	Disagree Strongly
1.	Less difficulty falling asleep					
2.	Less waking up at night					
3.	Better sleep throughout the night					
4.	Waking up feeling rested					
5.	Less fatigue during the day					
6.	Increased productivity					
7.	Increased energy					
8.	Increased ability to focus					
9.	Increased sense of overall well-being					
10.	Less feelings of frustration/restlessness/irritability					
11.	Less feelings of sadness					
12.	Less feelings of embarrassment or self-consciousness that I had to breathe through my mouth instead of my nose					
13.	Missing fewer activities with family and friends					
14.	Missing fewer days at work					

**Compared to before you had the procedure, how often do you suffer from the following conditions?**

		Very Rarely/ Never	Rarely	Occasionally	Frequently	Very Frequently
1.	Headaches					
2.	Sinus infections					
3.	Sore throat					
4.	Post nasal drip					

**Compared to the time prior to when you had the procedure, how often have you used each of the following products to help you with nasal congestion/difficulty breathing through your nose?**

		Much less frequently	Less frequently	About the same	More Frequently	Much More Frequently
1.	Oral medications (antihistamines, oral decongestants)					
2.	Nasal sprays (nasal steroids, inhaled decongestants)					
3.	Nasal breathing strips (for example, BreatheRight® Strips)					

**Figure 1. Aerin Medical Quality of Life survey.**

## 5 STATISTICAL ANALYSIS

Statistical methods are described within the outcome specific subsections that follow. Each subject served as their own control for comparison of preprocedure to postprocedure condition.

### 5.1 Analysis Populations

All eligible subjects who provided informed consent and completed at least 1 survey will be included in the analysis population. A second nonenrolled population will be defined as those subjects enrolled in the TP258 study that chose not to enroll in this extended follow-up study. The purpose of the nonenrolled population is to allow comparison of characteristics of subjects who self-selected to enroll in the follow-up study with those who chose not to enroll in the follow-up study.

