### 2.3 Study Design and Objectives

This is a prospective, non-randomized, multicenter follow-up study to collect long term data on a cohort of patients who participated in the Aerin Medical TP 258 study, “A Prospective, Multi-Center, Non-Randomized Study to Evaluate Treatment of Nasal Airway Obstruction Using the Aerin Medical Device.” The study will be conducted in a maximum of 8 centers. Follow-up data will be collected at the 12, 18 and 24-month post-procedure timepoints for all patients who have completed the above-mentioned study. The objective of the study is to evaluate the long-term durability of benefits associated with the Vivaer Stylus procedure.

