### 2.4 Subject Population

The subjects in this study will all have completed participation in the TP 258 Nasal Obstruction study at each center. All subjects will be willing to and agree to participate. Of the original 50 patients in the pivotal trial, 49 would be eligible to participate.

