### 5.6 Demographics and Baseline Characteristics

Demographic and baseline data are available from the TP258 study and will be summarized separately for the enrolled analysis population and the nonenrolled population and examined for potential differences between enrollees and nonenrollees. Discrete variables will be described as frequencies and percentages at each level of the categorical variable. Continuous variables will be summarized descriptively (n, mean, median, standard deviation, minimum, and maximum).

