### 5.7 Primary Analysis

Mean NOSE scores at baseline and each follow-up evaluation will be calculated to show the time course progression of improvement. Repeated measures analysis of variance (ANOVA) will be used to test for differences from baseline to follow-up evaluations. The statistical significance level will be set at 5% (p-value < 0.05).

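### Self-selection into the follow-up is tabulated but not carried into the NOSE durability estimate, although TP258 scores for all 49 completers could support an adjusted analysis

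*SAP*

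**What the plan says.** Protocol 2.3 plans data collection at the three "timepoints for all patients who have completed the above-mentioned study". Protocol 2.4 gives the number: "Of the original 50 patients in the pivotal trial, 49 would be eligible to participate". SAP 3.2 (Population and Sample Size) agrees: "The maximum sample size for this extended follow-up of the TP258 study was 49 subjects, the number that completed the TP258 study".

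SAP 5.1 restricts the analysis population to those who consented and returned at least one survey. It also defines a nonenrolled group and gives its role: "The purpose of the nonenrolled population is to allow comparison of characteristics of subjects who self-selected to enroll". The only analysis of that group is in SAP 5.6, which begins "Demographic and baseline data are available from the TP258 study" and plans separate summaries for the two groups and a look for differences.

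The primary analysis in SAP 5.7 is a repeated measures ANOVA, introduced by "Mean NOSE scores at baseline and each follow-up evaluation will be calculated". It has no weighting, adjustment or model that includes non-enrollees. SAP 5.3 plans no imputation for the primary analysis and leaves an imputation sensitivity analysis optional. It speaks of missed items and surveys, and does not name non-enrollees.

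On what TP258 recorded, SAP 4.1 says the NOSE questionnaire "was used in the TP258 study as the primary outcome measure", and SAP 3.2 describes the eligible subjects as "completing 26 weeks of follow-up in the Aerin Medical TP258 study".

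**The concern.** The objective (SAP 2, Protocol 2.3) is durability of benefit, and nothing in either document confines it to people who volunteer for a second study. If willingness to join is related to how well a subject was doing at week 26, the enrolled-only means and changes differ systematically from those of the 49. There is no control group or blinding (SAP 3.1), so the design offers no other check.

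The planned comparison does not settle the matter. It cannot be expected to detect moderate selection in a cohort this small. SAP 5.6 names demographic and baseline data but not week-26 NOSE, a plausible driver of willingness to continue. No rule says what follows if the groups differ. What is at stake is how large the 24-month benefit is said to be, and for whom.

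**Working it through.** **Plan's own figure.** 49 is a head count (50 patients in TP258, 49 completers) and agrees between Protocol 2.4 and SAP 3.2. No power, SD or expected enrolment rate is given, so there is nothing else to reproduce.

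**1. Identity, with no model.** Let m be the number of non-enrollees and g the shortfall in their mean improvement. Then mean over 49 = enrollee mean − (m/49) × g. With m = 10: 10/49 = 0.204, so g = 10 gives an overstatement of 2.0 points and g = 20 gives 4.1. With m = 5 the same two values give 1.0 and 2.0. Both m and g are unknown.

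**2. What the planned comparison can detect.** For 80% power at two-sided 0.05, the detectable difference in SDs is (1.96 + 0.84) × √(1/m + 1/(49 − m)).
- m = 10: 2.80 × √(0.100 + 0.0256) = 0.99 SD. Power for a 0.5 SD difference is 29%.
- m = 20: 2.80 × √(0.050 + 0.0345) = 0.81 SD. Power for a 0.5 SD difference is 41%.

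A table showing no clear difference is therefore likely even under moderate selection.

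**3. Bias if enrolment depends on week-26 NOSE.** All of these inputs are assumptions:
- SD 20 at every visit
- week-26 to month-24 correlation ρ of 0.5 to 0.7
- correlation r₀ of baseline with both later scores of 0 or 0.3
- odds of enrolling multiplied by 0.61 to 0.22 per SD worse week-26 score (log odds ratio b of −0.5 to −1.5)

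Let x be the standardised week-26 score and p(x) = 1/(1 + exp(−a − bx)), with a set so that the average of p is the enrolment rate. Enrollees' mean week-26 score is shifted by δ = E[x·p(x)]/E[p(x)] SDs. For jointly normal scores:
- bias in the month-24 mean = ρ × 20 × δ
- bias in the baseline mean = r₀ × 20 × δ
- bias in change = (ρ − r₀) × 20 × δ

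SAP 5.7 tests change from baseline, so the last line is the relevant one. In absolute size, with the low end at odds ratio 0.61 and ρ = 0.5 and the high end at 0.22 and ρ = 0.7:

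| Enrolment | δ (low, high) | Change, r₀ = 0 | Change, r₀ = 0.3 |
|---|---|---|---|
| 90% | 0.049, 0.122 | 0.5–1.7 | 0.2–1.0 |
| 80% | 0.096, 0.227 | 1.0–3.2 | 0.4–1.8 |
| 60% | 0.189, 0.427 | 1.9–6.0 | 0.8–3.4 |

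Example at 80%, r₀ = 0.3: 0.2 × 20 × 0.096 = 0.4 and 0.4 × 20 × 0.227 = 1.8. Simulation of 49 subjects at 80% enrolment gave 0.9–3.2 (r₀ = 0) and 0.4–1.9 (r₀ = 0.3), which agrees with the formula within simulation error.

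**4. What adjustment recovers.** Conditioning on baseline and week-26 NOSE of all 49 cut the bias in change to 0.14 points or less at about 80% enrolment and slightly lowered the sampling SD. This holds when selection acts through week-26 NOSE. A separate simulation let enrolment depend on week-26 improvement and also on the part of later improvement that week 26 does not predict (ρ = 0.6, log odds ratio 0.7 per SD for each). There the bias in mean improvement fell only from 3.3 to 1.9 points at 20% non-enrolment, and from 6.5 to 4.0 at 40%.

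**The case against.** The SAP is open about selection, and analysing those who consent to a voluntary extension is a legitimate choice. Protocol 2.4 itself says that participants will be those willing to take part. That is a fair defence of the primary analysis, but it does not supply a conclusion limited to volunteers, and neither document contains one.

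SAP 5.3 might be said to cover the gap. It is discretionary, names no method, and concerns surveys missed by people in the study.

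Several stronger readings are tempting, and the documents do not support them:
- **That the result is biased in the sponsor's favour.** The sign of selection is unknown. Subjects with poor results might be less willing to return, or might want continued contact.
- **That the bias in the month-24 mean is the bias in the primary result.** With r₀ above 0, enrollees also start lower and part of the bias cancels in the change from baseline.
- **That the bias can be judged against 15 points.** SAP 4.1 uses that threshold to classify individuals. It is not a margin for a group mean.
- **That the plan discards week-26 scores it is known to hold.** SAP 5.6 states only that demographic and baseline data are available. Week-26 NOSE is inferred from TP258's outcome and length of follow-up.
- **That statistical significance is in doubt.** A large improvement would probably remain significant.

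Two technical points also stand. The near-zero residual bias in the main simulation follows largely from adjusting on the same variable that generated enrolment. And an unstructured covariance over five visits has 5 × 6/2 = 15 parameters, which is many for 49 subjects with fewer contributing later visits, so the model needs a small-sample method and a fallback.

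**Conclusion.** The gap is real. Self-selection is named in the SAP, described in one comparison, and then plays no part in the durability estimate, although a modest supportive analysis could use information that should exist for all 49.

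At 80% enrolment the enrolled-only month-24 change would be off by about 0.4 to 1.9 NOSE points with a baseline correlation of 0.3, and by about 0.9 to 3.2 with none. The bias is smaller at higher enrolment and larger at lower. These figures rest on the assumed SD, correlations and strength of selection; they illustrate and do not predict. The point bears on the size of the estimate and the population it applies to. It does not invalidate the primary analysis.

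**What to change.** 1. **SAP 5.6:** add week-26 NOSE, and its change from baseline, to the enrolled versus nonenrolled comparison. First confirm that these scores can be obtained for non-enrollees.
2. **SAP 5.7:** add a supportive likelihood-based mixed model fitted to all 49 TP258 completers. The outcomes are NOSE at baseline, week 26 and months 12, 18 and 24. Use an unstructured covariance with Kenward-Roger degrees of freedom, and name a simpler structure in advance for use if the model does not converge. Non-enrollees contribute baseline and week 26. Report the model-based month-24 change for the 49 beside the enrolled-only result, and state the number enrolled.
3. **If week-26 scores are unavailable:** say so and limit the durability conclusion to enrollees.

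The cost is one added model and one added comparison, with no new subjects or contacts, plus retrieval of week-26 scores if they are not already in the dataset. The model removes only selection explained by the recorded scores, and its estimate may be slightly less favourable than the enrolled-only one.
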